3 THEORETICAL FRAMEWORK

4 RESEARCH QUESTION/AIM(S)

Objectives: To assess if pre-operative cardiopulmonary exercise testing is useful and effective in predicting at risk participants for post-operative morbidity and mortality, who undergo Whipple's surgery.

DATA ELEMENTS

1. Participant flow

Recruitment Details:

Participants for the study will be identified from a prospectively maintained database, by database search from April 2016 to March 2020, online records, clinical portal and Somerset cancer registry. Duplicates will be removed, cases will be screened.

This is a single centre study, to be done at, Royal Blackburn Hospital, East Lancashire Hospitals NHS trust, a District general Hospital in North of England. The study will be carried out in the department of General and HPB surgery, in liaison with Department of anaesthesia. This is the HPB referral centre for Lancashire and South Cumbria and incorporates participants referred for pancreatic surgery from three hospital trusts (Lancashire Teaching, University Hospital Morecambe Bay and Blackpool Teaching Hospitals).

Arm/Group Information:

The study will have two groups of participants, one who have undergone CPET pre-operatively and the other who have not undergone CPET.

Group 1 – Participants who have undergone CPET as a part of pre-operative assessment as well as P-POSSUM score calculation for predicting post-operative morbidity and mortality.

P-POSSUM is a scoring system for general elective and emergency surgeries which takes into account various physiological and operative parameters to calculate risk of morbidity and mortality in terms of percentages.

Group 2 – Participants who have not undergone CPET as a part of pre-operative assessment rather have only P-POSSUM calculated for predicting post-operative morbidity and mortality.

Period of Overall Study:

The study was conducted from February 2021 to March 2022. The database search was conducted and data collated. The study was conducted in one stage over a year.

Participants:

143 participants were recruited for the study during a period of 1 year. Out of 143 participants, 30 participants had undergone CPET as a part of pre-operative assessment.

2. Baseline Characteristics:

Baseline Analysis Population Information:

Data on baseline characteristics included age, sex, comorbidities, Rockwell frailty score, ASA grade, BMI.

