Data on study specific characteristics included dates of admission and discharge, diagnosis, details of surgery undergone, details of morbidity using Clavien-Dindo classification and mortality. Details of CPET and its measures as well as P-POSSUM scores were collated.

CPET specific data collected:

- 1) Exercise induced ST ischaemia- yes/no
- 2) VO₂ peak: actual and predicted
- 3) Anaerobic threshold:
- 4) VE/VCO₂:
- 5) Pulmonary function test- normal/ obstructive/ restrictive
- 6) Duration of pedalling bike
- 7) 30 day predicted risk

3. Outcome Measures:

Primary Outcome measures:

Primary outcome was measured in terms of CPET/P-POSSUM predicted mortality compared to actual 30 day mortality.

- In-hospital mortality
- 30 days
- 90 days

Secondary outcome measures:

Secondary outcome was measured in terms of CPET/ P-POSSUM predicted morbidity compared to actual morbidity (Clavien-Dindo grade 3 and above).

Morbidity in terms of:

- Post-operative pancreatic fistula
- Biliary fistula
- Delayed gastric emptying
- Bleeding
- Intra-abdominal collection
- Renal failure
- Cardiac complications
- Pulmonary complications
- Pulmonary embolism /DVT

The occurrence of morbidity and mortality were measured in terms of numbers and percentages. The calculated risk of morbidity and mortality by CPET and P-POSSUM are in terms of percentages, ranging from 0 to 100%, higher the percentage leading to worse outcome.

Statistical analyses overview:

The baseline characteristics were analysed using percentages and frequencies (mean, median, mode, standard deviation). Chi-square test was used to assess if the two study groups were

comparable. The p-value calculated was considered significant if <0.05 and confidence interval of 95%.

The study specific measures were analysed using parametric and non-parametric tests and binary logistic regression analyses to compare predicted to actual mortality and morbidity, between the participants who have had CPET and those who have not.

Univariate and multivariate analysis were done to assess if CPET measures could be used to predict occurrence of post-operative complications and morbidity.

4. Adverse Event information:

This was a retrospective review of a prospectively maintained database.

No adverse events were overcome during the time of the study

5. Limitations and Caveat:

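### Predicted morbidity with no stated severity limit is compared with observed Clavien-Dindo grade 3 and above; if the prediction covers any grade, an accurate predictor would appear to over-predict.

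*Combined protocol and SAP*

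**What the plan says.** All references are to the combined protocol and SAP.

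- **Secondary outcome** (3. Outcome Measures): "Secondary outcome was measured in terms of CPET/ P-POSSUM predicted morbidity compared to actual morbidity (Clavien-Dindo grade 3 and above". The grade limit qualifies the actual morbidity and is not attached to the prediction. The list of morbidities that follows (pancreatic fistula, delayed gastric emptying, pulmonary embolism/DVT and so on) carries no grades.
- **Predicted side.** Arm/Group Information says that P-POSSUM "takes into account various physiological and operative parameters to calculate risk of morbidity and mortality in terms of percentages". 3. Outcome Measures adds: "The calculated risk of morbidity and mortality by CPET and P-POSSUM are in terms of percentages, ranging from 0 to 100". Neither sentence names a severity.
- **CPET-derived risk.** The list of CPET data has one predicted quantity, "30 day predicted risk", without an event or a grade.
- **Observed data** (2. Baseline Characteristics): the study collected "details of morbidity using Clavien-Dindo classification and mortality", with no stated restriction on grade.
- **Analysis** (Statistical analyses overview): parametric and non-parametric tests and "binary logistic regression analyses to compare predicted to actual mortality and morbidity", with significance at p < 0.05.

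No section restricts, rescales or recalibrates the prediction to grade 3 and above, or plans a parallel any-grade comparison. 5. Limitations and Caveat mentions only the retrospective design and the small CPET group.

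**The concern.** Setting a predicted percentage against an observed percentage is a question of calibration, and the answer can be interpreted only if both sides count the same event. Here a patient whose worst complication is graded 1 or 2 has had morbidity in the ordinary sense of the predicted figure, but is scored as having had none. Any gap between predicted and actual then mixes two things: real miscalibration of the tool, and the share of complications that fall below grade 3. A reader could conclude that P-POSSUM overstates risk after pancreatoduodenectomy when the gap comes from the endpoint definition.

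**Working it through.** **No design figure to reproduce.** The documents give no predicted morbidity rate, no any-grade morbidity rate and no power calculation. The size can therefore only be illustrated.

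**Inputs from the documents.** There were 143 participants, 30 of them with CPET (Participants). The significance level is 0.05; sidedness is not stated, and I take it as two-sided. Forty participants are reported with a grade III intra-abdominal collection (8. Results of the study).

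**Assumed inputs.**
- p is the true risk of morbidity of any grade, predicted without error; range 40–70%, central case 50%.
- s is the share of affected patients whose worst grade is 3 or above; values 0.9, 0.8 and 0.6.

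**Step 1: expected ratio.** Expected predicted events are n × p and expected observed events are n × p × s. Observed/expected is therefore (n × p × s)/(n × p) = s. Whenever s < 1 the shift is towards apparent over-prediction.

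**Step 2: chance of a false finding.** Test the observed count against p with an exact binomial lower tail of 0.025. With n = 143 and p = 0.50, 143 × 0.50 = 71.5 events are predicted, and over-prediction is declared at 59 or fewer. The chance of that is P(X ≤ 59) with X ~ Binomial(143, 0.50 × s).

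| s | Expected grade ≥3 events | O/E | Chance of significant over-prediction |
|---|---|---|---|
| 1.0 (matched events) | 71.5 | 1.00 | 2% |
| 0.9 | 64.4 | 0.90 | 21% |
| 0.8 | 57.2 | 0.80 | 65% |
| 0.6 | 42.9 | 0.60 | 99.8% |

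**Step 3: sensitivity to p.** With n = 143 and p from 40% to 70%, the chance is 15–39% at s = 0.9, 49–92% at s = 0.8 and 98–100% at s = 0.6. In a group of 30, the size of the CPET group, with p = 50%, it is 7%, 18% and 59%. Those figures apply to any any-grade predictor evaluated in that group; they do not assume that the CPET risk is one.

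**Step 4: what the reported results allow.** The 40 grade III collections put the grade ≥3 rate at no less than 40/143 = 28.0%. (The documents print 28.2%, which fits 40/142.) The lowest s compatible with this is 0.280/p: 0.70 at p = 40%, 0.56 at p = 50%, 0.47 at p = 60% and 0.40 at p = 70%. So s = 0.6 is compatible with p = 50% or more, but not with p = 40%. This gives a floor for s, not an estimate of it.

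**The case against.** The strongest objection is that the premise is drawn from silence. The documents give P-POSSUM a one-sentence description and never define the event behind its percentage. An unstated severity is not the same as all severities. If the prediction already targets major morbidity, the bias vanishes, and switching the observed side to any grade would create apparent under-prediction instead. This stands: the conclusion must be conditional, and the predicted event must be defined before the observed one is changed. It does not remove the point, because the plain reading of an unqualified risk of morbidity is any grade and the plan offers nothing to the contrary.

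Four further limits also stand.

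- **CPET.** The direction is unknown, because the listed 30-day risk has no stated event or grade. A reader might infer that the mismatch would make CPET falsely look better than P-POSSUM. The documents do not support that: a false ranking needs the two predictions to be mismatched to different degrees, and nothing shows this.
- **Regression and discrimination.** A reader might also infer that the logistic regressions are biased. A difference in average level does not invalidate a regression of grade ≥3 morbidity on predicted risk, and odds ratios or ranking need not shift in this direction. Grade 3 and above is a legitimate endpoint for asking whether a tool identifies patients at risk.
- **Specification.** The plan names no observed/expected ratio. It does, however, define the outcome as predicted compared with actual, so a comparison of levels is within its terms.
- **Reported results.** 8. Results of the study reports no predicted-versus-actual morbidity and no over-prediction. Its conclusion, on anaerobic threshold and intra-abdominal collection, does not rest on this comparison.

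**Conclusion.** The point holds in conditional form. As written, the secondary outcome limits severity on one side of a predicted-versus-actual comparison. If the predicted percentage covers morbidity of any grade, an accurate tool would show an observed/expected ratio of s, below 1 whenever some affected patients stay under grade 3. In the assumed central case even a mild mismatch (s = 0.9) raises the chance of a false over-prediction finding about tenfold, from about 2% to about 21%.

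This rests on the any-grade reading, the assumed p and s, and a two-sided test at 0.05. The stronger statement, that an accurate predictor *would* be made to look wrong by a known amount, goes beyond the documents, because neither the predicted event nor any rate needed to size the bias is given. The point is firmest for P-POSSUM and concerns calibration only. It should be corrected before any predicted-versus-actual morbidity result is reported.

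**What to change.** 1. State, for P-POSSUM and for the CPET-derived risk separately, the event, grade and time window that the percentage targets.
2. Compare predicted with actual rates only against that same event. Where the prediction is of morbidity without a severity limit, tabulate any-grade Clavien-Dindo morbidity as the matched observed outcome. Alternatively, recalibrate the prediction to grade 3 and above and say so.
3. Keep grade 3 and above as a separate severe-morbidity outcome, used to assess discrimination.
4. Draw no conclusion about over-prediction from a comparison in which the two sides count different events.

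**Cost.** This takes a change to the outcome wording and one re-tabulation, which appears feasible because Clavien-Dindo details were collected with no stated grade restriction. The documents do not confirm that grades 1–2 were recorded completely, and retrospective notes may miss some of them. Under-recording would itself lower the any-grade count, so it should be stated as a limitation.

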With the above mentioned background, we aim to do a retrospective analysis of participants who have undergone pancreatic resections, at our centre. The aim is to assess the ability of physiological parameters assessed by CPET, in predicting post-operative morbidity and mortality. This study also aims at evaluating and analysing a comparator group of participants who did not have CPET and assess their perioperative outcomes, in particular post-operative complications, with those who had CPET.

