This was a retrospective review of a prospectively maintained database. The participants who underwent CPET was small compared to participants who did not. A prospective study with a large sample size is required to obtain more reliable results.

6. Certain Agreements:

All PIs are employees of Sponsor.

There is no specified results disclosure agreement between the PIs and sponsor.

7. Results Point of Contact

Name: Miss [name] (Principal Investigator)

Organization Name: East Lancashire Hospitals NHS Trust

[contact]

Email Id: [contact]

8. Results of the study

143 participants had Pancreatoduodenectomy during the study period. CPET was performed in 30 participants (21%). The participants' age was 67 ± 9 (Mean \pm SD). Forty participants (28.2%) had developed intra-abdominal collection (Clavien-Dindo III). In the CPET subgroup, Anaerobic Threshold (AT) ≤ 14 on CPET was a risk factor to develop intra-abdominal collection, according to univariate analysis (60% Vs 9%, p-value 0.02) and multivariate analysis (HR 3.5, 95% CI 1.6-657, p-value 0.02). Another significant risk factor was post-operative pancreatic leak (POPF) (40% Vs 22%, p-value 0.04).

By this study we concluded that participants who have Anaerobic Threshold ≤ 14 on CPET, are more likely to develop intra-abdominal collection requiring drainage after Pancreatoduodenectomy. This group of participants will be less likely to start chemotherapy early.

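### A chi-square test at p<0.05 cannot show that the CPET (30) and non-CPET (113) groups are comparable, and the between-group regression names no covariates

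*Combined protocol and SAP*

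**What the plan says.** All references are to the combined protocol and SAP.

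- **Aim.** Section 2 (Rationale): "This study also aims at evaluating and analysing a comparator group of participants who did not have CPET and assess their perioperative outcomes". The comparison of complications with the CPET group is therefore a stated aim.
- **Groups.** Section 4, Participant flow, defines the groups only by whether CPET was done: "Out of 143 participants, 30 participants had undergone CPET as a part of pre-operative assessment". It does not say how patients came to be selected for CPET. Both groups have P-POSSUM.
- **Design.** "This was a retrospective review of a prospectively maintained database".
- **Baseline data.** Section 4, Baseline Characteristics: "Data on baseline characteristics included age, sex, comorbidities, Rockwell frailty score, ASA grade, BMI".
- **Comparability check.** Section 4, Outcome Measures, Statistical analyses overview: "Chi-square test was used to assess if the two study groups were" comparable, with significance at p<0.05. Baseline data are otherwise summarised descriptively.
- **Outcome comparison.** The same section names parametric and non-parametric tests and binary logistic regression to compare predicted with actual mortality and morbidity "between the participants who have had CPET and those who have not". A multivariate analysis is named separately, to see whether CPET measures predict complications. Neither model has a covariate list.
- **Limitations.** The section admits that the CPET group is small. It does not mention selection for CPET or confounding.

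**The concern.** A significance test of baseline balance answers a question that depends heavily on sample size. With 30 participants in one group, a difference in age, frailty or ASA grade large enough to affect outcome can easily give p>0.05. Reading that as comparability takes lack of evidence of a difference for evidence of no difference.

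This matters because having CPET was not assigned by chance. If fitter or frailer patients were preferentially sent for the test, a difference in complications between the groups could reflect that selection. The usual protection is to adjust for measured pre-operative risk whatever the balance test shows, and the document does not say whether this was done.

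Chi-square is also the only comparability test named. It suits categorical characteristics. Using it for age or BMI would mean cutting them into categories, and none are given.

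**Working it through.** **1. Inputs and the plan's own figure.** Total 143 and CPET group 30 (Participant flow; Results). 30/143 = 20.98%, which reproduces the printed 21%. Comparator: 143 − 30 = 113. Significance level 0.05 (Statistical analyses overview). SD of age 9 years (Results). The document gives no baseline data by group and no power calculation for this check, so the prevalences below are assumptions shown over a range.

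**2. Worked example for a binary characteristic, 65% (CPET) versus 50% (non-CPET).**
- Pooled proportion: (30×0.65 + 113×0.50)/143 = 0.531.
- Standard error under no difference: √[0.531×0.469×(1/30 + 1/113)] = 0.1025.
- Standard error under the alternative: √[0.65×0.35/30 + 0.50×0.50/113] = 0.0990.
- Power: Φ[(0.15 − 1.96×0.1025)/0.0990] = Φ(−0.51) = 30%.

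Exact enumeration of the uncorrected Pearson chi-square over all outcomes of the two binomials gives 31%, or 24% with Yates correction (the plan does not say which is used). With the direction reversed (CPET 50%, non-CPET 65%), the two standard errors are 0.0998 and 0.1017, and the formula gives Φ(−0.45) = 33%. Direction makes little difference here.

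**3. Range for a binary characteristic.** Exact power, uncorrected, with the higher prevalence in the CPET group:

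| Non-CPET prevalence | +10 points | +15 | +20 | +25 | +30 |
|---|---|---|---|---|---|
| 10% | 33.8% | 56.4% | 75.7% | 88.6% | 95.5% |
| 20% | 24.0% | 42.5% | 62.2% | 78.8% | 90.0% |
| 30% | 19.2% | 34.9% | 53.8% | 71.9% | 85.9% |
| 40% | 17.2% | 31.9% | 50.6% | 69.7% | 85.0% |
| 50% | 16.2% | 31.0% | 50.8% | 71.5% | 87.7% |

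By the normal approximation, 50% power is reached at 13.5 to 20.1 points and 80% power at 21.7 to 28.2 points, depending on prevalence. Yates correction lowers every entry; for example, 70% versus 50% falls from 51% to 42%.

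**4. Continuous characteristic.** The standard error of a standardised difference near zero is √(1/30 + 1/113) = 0.2054. Power is Φ(d/0.2054 − 1.96):
- d = 0.2 (1.8 years of age at SD 9): 16%.
- d = 0.3 (2.7 years): 31%.
- d = 0.5 (4.5 years): 68%.
- 50% power at 1.96×0.2054 = 0.40 SD (3.6 years).
- 80% power at (1.96 + 0.84)×0.2054 = 0.58 SD (about 5.2 years).

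**5. Would a fixed cut-off on the standardised difference be better?** Not at this size. With no underlying difference, the chance that an observed value exceeds 0.2 in either direction is 2×[1 − Φ(0.2/0.2054)] = 33%; for 0.1 it is 63%. Over six variables, if independent, at least one exceeds 0.2 with probability 1 − 0.67⁶ = 91%. The estimate and its interval (about ±0.40 SD) are informative; a threshold is not.

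**6. Room for adjustment.** The only cohort-wide event count printed is 40 intra-abdominal collections. A model with CPET group plus all six baseline variables has at least 7 parameters, so at most 40/7 = 5.7 events per parameter. No death count is printed.

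**The case against.** The strongest reply has five parts.

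1. **Large imbalances would usually be found.** This stands. At 25 points, uncorrected power is about 70% to 89% over the assumed range, and at 0.5 SD it is 68%. A reader might infer that the test usually misses any real imbalance; that is true only below the sizes given above.

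2. **The plan does name a regression.** This stands in part. A reader might infer that the between-group comparison was unadjusted. The document does not support that: logistic regression is named and its covariates are simply unstated. Nor does the document say that a non-significant chi-square leads to an unadjusted comparison.

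3. **Predicted-versus-actual comparison already carries case mix.** This also stands in part. P-POSSUM is available in both groups and uses physiological information. But the plan does not present it as adjustment of the CPET versus non-CPET contrast, and the score also contains operative parameters, which arise after the pre-operative test.

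4. **Age and BMI may not have been categorised.** Correct: no categories are described, and age is reported as mean and SD. The concern about cut-points is conditional on chi-square being applied to them.

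5. **The reported conclusion is untouched.** Correct. The anaerobic-threshold finding compares participants within the CPET subgroup, and no CPET versus non-CPET result is reported.

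None of this makes a non-significant p-value evidence of comparability.

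**Conclusion.** The concern holds in a bounded form. With 30 versus 113, the chi-square check has less than even power for imbalances below about 14 to 20 percentage points or 0.4 SD, so p>0.05 cannot justify treating the groups as alike. Whether the collected baseline data were used to adjust the comparison cannot be determined from the document.

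The size rests on assumed prevalences of 10% to 50% in the comparator, a two-sided 5% level, no continuity correction, and a common SD for continuous variables (9 years for age, from the whole cohort). Yates correction would make the test weaker still.

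A reader might go further and infer that the groups were in fact imbalanced, or that the comparison is in fact confounded. The document prints no baseline data by group, so neither is shown. The point is worth acting on because the comparison is a stated aim and the repair uses existing data.

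**What to change.** - **Balance.** Replace the chi-square comparability verdict with standardised differences and 95% confidence intervals for each baseline variable, keeping age and BMI continuous. Use no pass/fail cut-off.
- **Adjustment.** Whatever balance is shown, adjust the between-group outcome comparison in the logistic model already named. Use a small set of pre-operative variables (for example age and one of ASA grade or frailty), chosen on clinical grounds and written down before the model is run or re-run. Use Firth penalisation if events are sparse.
- **P-POSSUM.** If used as a covariate, use its physiological component. Label any model with the full score a sensitivity analysis, because that score includes operative parameters.
- **Reporting.** List the covariates in every model, describe the CPET versus non-CPET comparison as associational, and add confounding by selection for CPET to the limitations.

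**Cost.** A short re-analysis of data already collected, plus a few lines of text. The price is a wider confidence interval. For mortality, adjustment may be limited or impossible if deaths are few; the document gives no count, so this should be checked first.

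### The plan names no valid way to compare a predicted mortality percentage with 30-day death, and the literal reading of its tests would reject an accurate tool in the 30 CPET participants

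*Combined protocol and SAP*

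**What the plan says.** Under Outcome Measures: "Primary outcome was measured in terms of CPET/P-POSSUM predicted mortality compared to actual 30 day mortality". On the scale of the predictions: "The calculated risk of morbidity and mortality by CPET and P-POSSUM are in terms of percentages, ranging from 0 to 100" per cent. Each participant's actual outcome is death or survival.

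The Statistical analyses overview gives the method in one sentence: the study-specific measures were "analysed using parametric and non-parametric tests and binary logistic regression analyses to compare predicted to actual mortality and morbidity". The sentence goes on to place the comparison between participants with and without CPET. The significance rule is "The p-value calculated was considered significant if <0.05 and confidence interval of 95" per cent; sidedness is not stated. A chi-square test is mentioned, but for the comparability of the two groups.

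The section names no observed/expected ratio, calibration intercept or slope, AUC, or method for sparse events. On numbers, Participant flow says: "Out of 143 participants, 30 participants had undergone CPET as a part of pre-operative assessment". Neither the number of deaths nor a mortality rate appears anywhere.

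**The concern.** A predicted risk is a small positive percentage, whereas an actual outcome is 0 or 1. When death is uncommon, nearly every participant survives, so predicted minus actual is positive for nearly everyone even if the tool is exactly right. A signed-rank test responds to that imbalance of signs, not to whether the predicted total matches the observed total. A paired t-test does compare the totals, but in a small group with no deaths its standard error reflects only the spread of the predictions, so it rejects then as well.

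Logistic regression has a different weakness. With no deaths in the group being modelled, or with deaths perfectly separated by a predictor, the maximum-likelihood estimate is infinite.

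What is at stake is the primary comparison. It could yield a significant difference between predicted and actual for an accurate tool, or no usable estimate.

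**Working it through.** **Inputs.** From the document: 30 CPET participants, 143 in total, hence 143 − 30 = 113 without CPET; alpha 0.05. Assumed: a two-sided test, and 30-day mortality m of 2%, 3.3% (1/30), 5% or 10%. Expected deaths among 30 are then 0.6, 1.0, 1.5 and 3.0. The plan has no power or error-rate figure to reproduce.

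**Signed-rank test, n = 30, by hand.** The rank sum has mean 30×31/4 = 232.5 and SD √(30×31×61/24) = 48.6. Provided predicted risks are below 50%, each death gives a negative difference larger in size than any survivor's, so k deaths take the top k ranks.

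| Deaths k | Negative rank sum | z |
|---|---|---|
| 0 | 0 | −4.78 |
| 1 | 30 | −4.17 |
| 2 | 59 | −3.57 |
| 3 | 87 | −2.99 |
| 4 | 114 | −2.44 |
| 5 | 140 | −1.90 |

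The test therefore rejects whenever there are four or fewer deaths, whatever the predictions were. For a correct tool with mean risk m, the false-rejection rate is roughly P(Binomial(30, m) ≤ 4): 99.97%, 99.7%, 98.4% and 82.5% at 2%, 3.3%, 5% and 10%.

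**Simulation.** The tool is perfectly calibrated: risks are logit-normal (SD 0.5 or 1.0 on the logit scale), death is drawn with the predicted probability, and there are 1,000 cohorts per setting. Rejection rates at n = 30:

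| Mortality | Signed-rank | Paired t | z test, observed minus expected deaths |
|---|---|---|---|
| 2% | 99.9-100% | 54-56% | 3-5% |
| 3.3% | 99.4-99.7% | 35% | 5-6% |
| 5% | 98.2-98.6% | 21-23% | 4-5% |
| 10% | 83% | 8% | 5% |

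Further runs gave 85% for signed-rank at 10%, and 57%, 35%, 19% and 9% for the paired t-test. At n = 143 the signed-rank test rejects in 100% of runs from 2% to 10%, and the paired t-test in about 5-11%.

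Up to 5% mortality the paired t figures track the chance of no deaths, (1 − m)^30:
- 0.98^30 = 0.55
- (29/30)^30 = 0.36
- 0.95^30 = 0.21
- 0.90^30 = 0.04

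**Logistic regression for mortality.** At 2%, 3.3%, 5% and 10%:
- One predictor in the 30 CPET participants: no finite fit in 60-65%, 39-45%, 27-29% and 5-9% of datasets.
- All 143, predicted risk alone: no finite fit in 6-8%, 0.5-1%, 0% and 0%.
- All 143, predicted risk plus a CPET-group term: 61%, 40%, 22% and 5%. Most of this is the chance that one group has no deaths. At 3.3%, 113 without a death has probability (29/30)^113 = 0.022, so the chance that either group has none is 1 − (1 − 0.362)(1 − 0.022) = 0.38.

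**Contrast with morbidity.** The results give "Forty participants (28.2%) had developed intra-abdominal collection (Clavien-Dindo III"; 40/143 is 28.0%, and the printed 28.2% fits 40/142. At 28% and n = 30, one-predictor logistic regression always has a finite fit, the paired t-test rejects in 5% and the signed-rank test in 7-13%. Sparse data can still bite there: the CPET-subgroup result is "multivariate analysis (HR 3.5, 95% CI 1.6-657, p-value 0.02", an interval of extreme width.

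**The case against.** The strongest reply is that the plan names neither a signed-rank test nor a paired t-test. It names a class of tests, and valid methods fit the same words, such as an exact test of death counts, or a Mann-Whitney comparison of predicted risk between those who died and those who survived. That stands, and it is why the point concerns an unspecified method whose literal reading fails. The Mann-Whitney comparison measures discrimination, not whether predicted matches actual. It also has little power here: 3-12% rejection at n = 30 and 3.3% mortality, among simulated cohorts with at least one death.

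A second reply is that the sentence describes a comparison between CPET and non-CPET participants, not a within-person test. The sentence says both things. The between-group reading does not rescue the logistic model, because the group term is what makes it fail.

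Third, a reader might infer that the study obtained a wrong primary answer. The documents do not support that. The results section gives no predicted-versus-actual mortality result, and its conclusion concerns anaerobic threshold and intra-abdominal collection. Nor do they support saying that about one death occurred among the 30, or that logistic regression did fail: the death count is absent, so failure is a probability that falls as mortality rises.

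The Limitations section concedes that the CPET group was small, but not what this means for a mortality comparison.

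**Conclusion.** The concern holds as a specification gap in the primary analysis. The plan gives no valid calibration or discrimination method, and nothing elsewhere in the document supplies one. On the literal reading, a nominal 5% test in the 30 CPET participants has a false-rejection rate of about 98-100% (signed-rank, 2-5% mortality) or 83-85% (10%). For the paired t-test it is about 55%, 35%, 20% and 8% at 2%, 3.3%, 5% and 10%. Logistic regression for mortality is at risk in the CPET group, and in all 143 once the group term enters.

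These sizes rest on assumed mortality and on a paired test being the one used. The signed-rank result depends little on the spread of predicted risk, as the hand calculation shows.

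A reader might extend the criticism to the morbidity analysis, since the same sentence covers it. At about 28% for intra-abdominal collection, that is largely unsupported: single-predictor logistic regression is usable.

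This is a worthwhile, inexpensive correction and not an essential one, because the test is not named and no mortality conclusion was drawn from it.

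**What to change.** For mortality, replace the general sentence with a stated method:
- For each tool, among participants who hold that prediction, report observed 30-day deaths, the sum of predicted risks, and the observed/expected ratio with an exact (Poisson-binomial or Poisson) 95% confidence interval.
- Where there are deaths, report discrimination: AUC with its interval, or predicted risk in those who died versus survivors.
- Do not apply a paired t-test or signed-rank test to predicted percentage versus the 0/1 outcome. This does not bar the comparison of deaths with survivors.
- Use Firth penalisation for any logistic model of mortality, and fit none in a group without deaths.

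The same observed/expected summary may be reported for morbidity for consistency; ordinary single-predictor logistic regression can stay there.

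The cost is a wording change and a short re-analysis, since the CPET 30-day predicted risk and the P-POSSUM scores were already collected. The downside is wide intervals. For example, 1 death against 1.5 expected gives a ratio of 1/1.5 = 0.67; the exact Poisson limits for one event, 0.025 and 5.57, divided by 1.5, give about 0.02 to 3.7. That width is an honest statement of what 30 participants can show.
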